#### CBCT Healing Assessment and statistical analysis

Patients (GWS=12, EA=14), were recalled at 12 months postoperative, and the same imaging and clinical endodontic testing was done as had been performed preoperatively. A 3-D volumetric analysis using ITK Snap software (ITK SNAP, Philadelphia, PA) was completed

to measure the volume of pre-and-post-operative periapical findings in mm^3. Each individual root was then assigned a 3Droot classification of either healed (normal PDL around the root at recall), healing (reduced size of finding), or diseased (same or larger size finding). Pearson's Chi squared test was used to evaluate if there was any difference in 3Droot healing outcomes between the GWS and EA groups. Results were considered significant if the p≤.05.

Clinical tooth healing classification based on clinical examination and patient report (Ctooth)

Teeth were classified as being clinically successful if the patient had no symptoms other than mild tenderness to percussion. Teeth were not considered as failures due to mild percussion sensitivity alone, as long as the patient reported no pain when chewing.

Pearson's Chi squared test was used to evaluate if there was any difference in Ctooth healing outcomes between the GWS and EA groups. Results were considered significant if the p≤.05.

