**NCT# 04552132**

**May 2, 2022**

## Pain Assessment Protocol

This study protocol was approved by the Institutional Review Board of Saint Louis University, Saint Louis, MO (Protocol Number 31359). Patients were recruited for this study from the patients seen at the Center for Advanced Dental Education at Saint Louis University from September 2020 through March 2022. Informed consent was obtained from each patient for participation in this study. The following inclusion criteria were utilized for participation in the study: adults fully able to provide informed consent, with restorable, symptomatic molar teeth (reporting  $\geq 20$ mm on the VAS during the previous 24 hours) seeking endodontic therapy. Patients where both Ibuprofen and Acetaminophen were contraindicated, patients with chronic pain issues for which they regularly need to consume analgesics, and patients having taken analgesics or antibiotics within the previous 6 hours were excluded from this study.

The first patient treated in the study was randomized by coin toss, followed by an alternating pattern thereafter for the 2 groups: GentleWave (GWS) (n=16) or EndoActivator (EA) (n=17). Prior to their clinical evaluation, the patients marked on: 1) a 100mm VAS instrument where they felt best represented their degree of pain experienced at that moment, and 2) a 2nd 100mm VAS instrument their maximum level of pain during the previous 24 hours. Clinical evaluation of the patient included percussion and palpation testing, periodontal probing measurements, thermal pulp sensibility testing using a cold source (Endo Ice), and an evaluation of tooth mobility. Radiographic examination (XDR Radiology, Los Angeles, CA) included bitewing, straight-on periapical, angled periapical, and 4X4 cm high-resolution limited field of view cone beam computed tomography (CBCT) (CAREstream 9600-CAREstream Dental, Atlanta, GA) imaging.

Following the administration of topical anesthetic (20% Benzocaine), the same high-level of anesthetic was administered to all patients, in order to standardize the number of injections received by the participants. If supplemental anesthesia was required, intrapulpal injections were performed for vital teeth and periodontal ligament injections were performed for necrotic teeth.

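### The 12-month healing tests cover 26 of 33 patients, have no class for an extracted tooth, can count a retreated one as a success, and come with no sensitivity analysis for the seven unseen outcomes

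*Combined protocol and SAP*

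**What the plan says.** The *Pain Assessment Protocol* section gives the groups as "GentleWave (GWS) (n=16) or EndoActivator (EA) (n=17"), 33 patients in all, recruited "from September 2020 through March 2022". The document is dated May 2, 2022.

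The *CBCT Healing Assessment and statistical analysis* section then bases the healing outcomes on a smaller set: "Patients (GWS=12, EA=14), were recalled at 12 months postoperative". Two outcomes are defined there.

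- **3Droot**, per root, compares recall imaging with preoperative imaging. The classes are "healed (normal PDL around the root at recall), healing (reduced size of finding), or diseased (same or larger size finding").
- **Ctooth**, per tooth, rests on clinical examination and patient report: "Teeth were classified as being clinically successful if the patient had no symptoms other than mild tenderness to percussion".

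Each outcome is compared between arms by Pearson's chi-squared test. For Ctooth the text is "Chi squared test was used to evaluate if there was any difference in Ctooth healing outcomes between the GWS and EA groups", and the criterion is "Results were considered significant if the p≤.05". Whether a continuity correction applies is not stated.

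The section gives no reasons for the missing patients, no rule for an extracted or retreated tooth, no method for missing outcomes, no sensitivity analysis and no comparison of recalled with absent patients. It reports no healing counts.

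**The concern.** Two gaps act together.

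The first is in the definitions. Each outcome is read from a tooth examined or imaged at recall. An extracted tooth cannot be given any of the three 3Droot classes, and the Ctooth definition does not mention it, so it leaves the denominator instead of counting as a failure. A retreated tooth can still be examined. If it is free of symptoms it meets the Ctooth definition of success, although the treatment under study did not last. Both routes push the success rate upward if such cases occur, and the two arms need not be affected equally.

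The second is in the denominator. About a fifth of the patients contribute nothing to either test, and nothing shows how far the conclusion depends on them. Loss rates of similar size do not settle this, because the reasons can differ by arm. With 12 and 14 patients, a few unseen outcomes carry a lot of weight.

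At stake is whether a 12-month difference, or the lack of one, can be read as applying to the patients treated or only to those who came back.

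**Working it through.** The plan states no expected healing rate, power, dropout allowance or healing result, so there is no figure of its own to reproduce.

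**Inputs.** Patients in the trial: GWS 16, EA 17 (*Pain Assessment Protocol*). Recalled: GWS 12, EA 14; Pearson chi-squared; threshold 0.05 (*CBCT Healing Assessment and statistical analysis*). Assumptions: one tooth per patient, Ctooth scored as success or failure, no continuity correction unless stated.

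**Step 1: who is absent.**
- Total 16 + 17 = 33; recalled 12 + 14 = 26 (78.8%); absent 33 − 26 = 7 (21.2%).
- GWS 16 − 12 = 4, and 4/16 = 25.0%. EA 17 − 14 = 3, and 3/17 = 17.6%.

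**Step 2: range of the Ctooth risk difference.** Let x of 12 GWS and y of 14 EA teeth be successes.
- Most favourable to GWS: (x + 4)/16 − y/17.
- Least favourable to GWS: x/16 − (y + 3)/17.
- Width: 4/16 + 3/17 = 0.250 + 0.176 = 0.426, or 42.6 points, whatever x and y are.

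**Step 3: illustrations with the planned test.** The counts are hypothetical.

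| GWS | EA | What was changed | Pearson p |
|---|---|---|---|
| 12/12 | 10/14 | recalled patients only | 0.044 |
| 12/13 | 10/14 | one unseen GWS failure added | 0.163 |
| 15/16 | 13/17 | one unseen GWS failure, other six successes | 0.167 |
| 12/16 | 10/17 | all seven unseen are failures | 0.325 |
| 9/12 | 14/14 | recalled patients only | 0.047 |
| 9/12 | 14/15 | one unseen EA failure added | 0.183 |
| 9/16 | 14/17 | all seven unseen are failures | 0.103 |

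A non-significant table can also move. 12/12 v 12/14 has p = 0.17. The two extreme fills are 12/16 v 15/17 (75.0% − 88.2% = −13.2 points, p = 0.32) and 16/16 v 12/17 (100% − 70.6% = +29.4 points, p = 0.0185). The width is 13.2 + 29.4 = 42.6 points, as in Step 2.

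**Step 4: how common this is.** All 13 × 15 = 195 possible tables for 12 v 14 were enumerated; 94 have p ≤ 0.05 and 101 do not.
- One unseen outcome can remove significance in 20 of the 94 (21%) and create it in 6 of the 101.
- All seven, filled freely, can remove it in 70 of the 94 and create it in 64 of the 101.
- No fill of the seven turns a significant result into a significant one in the opposite direction.
- With continuity correction, one outcome changes 12 of 70 significant and 10 of 125 non-significant tables; all seven can change 58 of 70 and 58 of 125.

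These counts treat all tables as equally likely. Weighted by assumed true success rates, the share of significant results that one unseen outcome could undo is 86% at 95% v 80%, 70% at 95% v 70%, and 37% at 90% v 50%. The exposure is greatest where success is high and the true difference moderate.

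**3Droot.** This outcome counts roots in three classes, and the number of roots is not given. One absent patient can remove several correlated roots. No corresponding figure can be computed.

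**The case against.** The strongest reply is that nothing shows the seven absences have anything to do with outcome. No extraction or retreatment is mentioned anywhere. Recruitment ran to March 2022 and the document is dated 2 May 2022, so a patient treated after about May 2021 had not reached 12 months by that date. Some or all of the seven may simply not have been due. This stands: a reader might infer that the absent patients are hidden failures, or that the success rates are in fact biased upward, and the documents support neither. They do not exclude it either, which is why reasons by arm are needed.

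A reader might also infer that retreated teeth drop out of the analysis. The text does not say so. A retreated tooth seen at recall can be classed under both definitions; the risk is misclassification. Only extraction leaves a tooth without a class.

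Finally, much of the fragility comes from small numbers and the choice of test. Changing one observed outcome removes significance in 26 of the 94 tables, more than the 20 for one unseen outcome. The table 12/12 v 10/14 has a smallest expected count of 12 × 4/26 = 1.85. It is significant only by uncorrected Pearson: Fisher's exact test gives p = 0.10 and the corrected chi-squared p = 0.14, so under either there is no significance to lose. This too is correct, and it limits what the p-values can prove. It does not touch the 42.6-point range, which depends on no test, or the gap in the definitions.

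**Conclusion.** The point holds as a limited one. Both 12-month tests use 26 of 33 patients, without reasons for the other seven or any sensitivity analysis. The definitions leave an extracted tooth unclassed and let a retreated, symptom-free tooth pass as a Ctooth success. Either would overstate success if it occurred; whether either did is not stated.

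For Ctooth the unseen outcomes leave 42.6 points of possible movement in the risk difference, and in borderline tables a single one can carry p across 0.05. This assumes one tooth per patient and, for the p-values, Pearson's test without correction.

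A reader might go further and conclude that one unseen patient could reverse the trial's finding. The documents do not support that. One outcome can change whether the threshold is met, but even all seven cannot produce a significant result in the opposite direction. With no healing counts reported, the fragility of the actual result is not shown. Nor do the figures carry over to 3Droot. The matter is minor in severity but inexpensive to put right.

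**What to change.** 1. Account for all 33 patients at 12 months, by arm, with the reason for each absence, including not yet due.
2. State in the analysis how lost teeth are handled: any tooth known to have been extracted or retreated before 12 months is classed as diseased for 3Droot and as a clinical failure for Ctooth. List the reason for each.
3. For Ctooth, add a best/worst-case or tipping-point table over the outcomes that remain unseen. Use one stated test throughout, and say whether a continuity correction applies.
4. Report the 12-month conclusion beside that table, so that readers can see which unseen outcomes it depends on. A rule that a difference counts only if it survives the plausible part of the table is not needed, and would require a definition of plausible that the documents do not supply.

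The cost is a chart check and one small table. Each absent patient whose outcome becomes known narrows the range by 1/16 = 6.25 points (GWS) or 1/17 = 5.9 points (EA). The downside is that the stated 12-month conclusion may come out weaker.

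### The CBCT healing test treats roots as independent although treatment was allocated by patient, and it does not say which roots enter

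*Combined protocol and SAP*

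**What the plan says.** The Pain Assessment Protocol section makes the patient the unit of allocation: "The first patient treated in the study was randomized by coin toss, followed by an alternating pattern thereafter for the 2 groups". Those eligible were "adults fully able to provide informed consent, with restorable, symptomatic molar teeth", so a treated tooth normally has more than one root. A periapical lesion was not required for entry, and both vital and necrotic teeth were treated ("intrapulpal injections were performed for vital teeth and periodontal ligament injections were performed for necrotic teeth").

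The CBCT Healing Assessment and statistical analysis section gives the 12-month sample: "Patients (GWS=12, EA=14), were recalled at 12 months postoperative". Software was used "to measure the volume of pre-and-post-operative periapical findings" in mm³. The outcome is then set at root level: "Each individual root was then assigned a 3Droot classification of either healed (normal PDL around the root at recall"), with the other two categories being "healing (reduced size of finding), or diseased (same or larger size finding"). The analysis is one sentence: "Pearson's Chi squared test was used to evaluate if there was any difference in 3Droot healing outcomes between the GWS and EA groups", judged at p≤.05.

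The same section defines a separate tooth-level outcome, Ctooth. Nowhere do the documents describe a patient-level summary of 3Droot, a mixed model, GEE, a cluster-adjusted test or a permutation test. They give no root count and no rule on which roots enter.

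**The concern.** Pearson's chi-squared test takes each counted unit as an independent observation. Roots of one molar share the patient, the tooth, the session and the assigned arm, so their outcomes are likely to be positively correlated. Counting them separately then overstates the information and makes the 3Droot p-value too small.

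The secondary issue is the denominator. Healed is defined only by the appearance at recall. As worded, a root with no finding at either time is healed; read literally, it also fits the same-size part of the diseased definition. If such roots were counted as healed, they would dilute a real difference between arms, or bias the comparison if unevenly split. The preceding sentence, on measuring periapical findings, also permits the reading that only roots with a finding were classed. The unit-of-analysis problem is present under both readings.

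**Working it through.** The plan states no sample size, power or root count for this analysis, so there is no figure of its own to reproduce beyond the nominal 5%.

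**Inputs from the documents:** allocation by patient; 12 GWS and 14 EA patients at recall; three outcome categories per root; unadjusted Pearson test; p≤.05.

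**Assumed inputs:** one tooth per patient, 2-3 roots per tooth, the correlation within a patient, the category rates and the share of lesion-free roots.

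**1. Design effect.** With m roots per patient and intracluster correlation ICC on the observed scale, DE = 1 + (m−1)×ICC. Effective roots = 26m/DE. For the 2-df test, actual level = P(χ²₂ > 5.991/DE).

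| m | ICC | DE | Roots | Effective roots | Actual level |
|---|---|---|---|---|---|
| 2 | 0.3 | 1.3 | 52 | 40.0 | 10.0% |
| 2 | 0.5 | 1.5 | 52 | 34.7 | 13.6% |
| 3 | 0.3 | 1.6 | 78 | 48.8 | 15.4% |
| 3 | 0.5 | 2.0 | 78 | 39.0 | 22.4% |

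**2. Simulation, latent-normal model.** Settings: 12 v 14 patients, 2 or 3 roots with equal probability, healed/healing/diseased 50/35/15% in both arms, 40,000 null trials per setting. The correlations are on the latent scale, which is larger than the observed ICC: for a 50/50 binary outcome, latent 0.3, 0.5 and 0.7 correspond to about 0.19, 0.33 and 0.49.

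| Roots | 0.3 | 0.5 | 0.7 |
|---|---|---|---|
| (a) All had a lesion | 8.5% | 11.6% | 15.9% |
| (b) Half lesion-free, counted as healed, scattered at random | 5.2% | 6.1% | 7.8% |
| (b) Same, clustered by patient | 11.4% | 13.5% | 16.6% |
| (c) Half lesion-free, left out, scattered at random | 6.3% | 7.3% | 9.5% |
| (c) Same, clustered by patient | 8.0% | 11.0% | 15.1% |

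At correlation 0, (a) gives 5.0%. Clustered (b) is already about 9% at correlation 0, because lesion-free status is itself shared within a patient. Over four category mixes (50/35/15, 70/20/10, 33/33/33, 40/40/20), (a) runs 7.4-16.3%, and (b) 4.4-8.4% scattered or 7.3-20.0% clustered.

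**3. Simulation, second model.** A Dirichlet-multinomial model on the observed ICC scale (20,000 null trials per setting, 2 to 3 roots, outcome splits 60/30/10, 70/30 and 50/50) gives 4.6-5.4% at ICC 0, 8.2-15.1% at ICC 0.3 and 10.6-22.2% at ICC 0.5. The direction and order of size do not depend on one model.

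**4. Bounding example.** Two roots per patient, always concordant, healed or not:

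- Roots, 20/24 v 14/28: χ² = 52×(20×14 − 4×14)²/(24×28×34×18) = 6.34, p = 0.012 (Fisher 0.019).
- The same patients, 10/12 v 7/14: χ² = 26×(10×7 − 2×7)²/(12×14×17×9) = 3.17, p = 0.075 (Fisher 0.11).

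Counting each patient twice doubles χ² and moves the result across 0.05.

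**5. Dilution, only if lesion-free roots were counted as healed.** With half lesion-free, true rates of 80% v 40% become 0.5 + 0.5×0.8 = 90% v 0.5 + 0.5×0.4 = 70%. Simulated power of the planned test falls from 81-84% to 39-45%.

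**The case against.** The strongest objection is that the size is wholly assumed. The documents give no root count, correlation, category rates or lesion share, and the results run from no inflation (4.4%) to 20%. If lesion-free roots are scattered at random and counted as healed, the effect at 50/35/15 is small (5.2-7.8%). This stands: the text supports the statement that the test can exceed 5%, but no particular figure.

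The problem would also vanish if only one root per patient entered. The wording, applied to molars, argues against that, and the separate tooth-level outcome shows that the two units were distinguished.

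On eligibility, two of the three categories presuppose a finding, so restriction to lesion-bearing roots is a plausible reading. That also stands, and the dilution figures apply only under the other reading. The bounding example is binary and perfectly concordant, so it marks an extreme and is not an estimate.

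Finally, 3Droot is not named as primary. If its result was non-significant, correcting an inflated error rate would not reverse it, though dilution could still matter. This limits the severity. None of these objections supplies the missing clustering adjustment.

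**Conclusion.** The concern holds. The stated test breaks its own independence assumption, because patients were allocated and roots were counted. This follows from the text and is held with high confidence.

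Its size is conditional. With 2-3 roots per patient, all lesioned, and latent correlation 0.3 to 0.7, the false-positive rate is about 8.5% to 15.9%. It is close to nominal under the mildest assumptions and reaches 20% under the harshest. If any patient contributed more than one tooth, which the documents do not address, clustering would be stronger.

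The missing eligibility rule is a real gap in the outcome definition, but its effect depends on the reading, so that part is held with moderate confidence. The point should be fixed: it affects the inference on one outcome and can be repaired by re-analysis.

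**What to change.** **Unit of analysis.** Analyse 3Droot with the patient as the unit, and name one method before re-running. Permuting whole patients between arms on the planned 2x3 Pearson statistic keeps the three categories. Its simulated size was 4.2-5.3% across latent correlations 0.3, 0.5 and 0.7 with all roots lesioned, half lesion-free scattered, or half clustered. Alternatives over the same settings:

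- permuting patients on the share of lesion roots healed: 3.4-4.9%;
- all lesion roots healed, yes or no, with Fisher's test: 0.9-3.3% (conservative);
- a simple cluster-robust t test with patients minus 2 df: 5.0-5.6% with all roots lesioned but 6.0-7.3% with half lesion-free, so it would need a stronger small-sample correction.

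Permutation rests on treating patients as exchangeable, since allocation was one coin toss followed by alternation. State that assumption.

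**Eligible roots.** Restrict the comparison to roots with a pre-operative finding volume above 0 mm³ and report baseline-normal roots separately by arm; a separate no-finding category is another possibility. Restriction alone does not cure the clustering. In an illustration with a fixed, invented 8/12 v 5/14 lesion-free split and no treatment effect, it lowered the false-positive rate from 17/20/23% to 4.6/7.9/11.3% at correlation 0/0.3/0.5.

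**Reporting.** Give patients, teeth, roots and lesion-bearing roots per arm.

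**Cost.** A change of wording and a re-analysis of measurements already taken. The denominator shrinks, the p-value will probably rise if roots are positively correlated, and power is low. For 80% v 40% healed with half of roots lesion-free, permuting patients on the 2x3 statistic has 43-47% power (scattered) or 31-40% (clustered). With all roots lesioned it has 63-75%, against 81-84% for the planned test, part of which reflects that test's inflated error rate.

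### As written, the 3Droot comparison counts roots with no periapical finding before treatment as healed, which dilutes the device contrast and exposes it to baseline case mix

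*Combined protocol and SAP*

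**What the plan says.** The section on CBCT healing assessment uses ITK-SNAP "to measure the volume of pre-and-post-operative periapical findings" and then classifies by root: "Each individual root was then assigned a 3Droot classification of either healed (normal PDL around the root at recall". The other two categories are "healing (reduced size of finding), or diseased (same or larger size finding". The condition for healed concerns the recall image only. Nothing is said about the state of the root before treatment, and no rule excludes, separates or adjusts for roots without a preoperative finding. The arms are compared with an unadjusted Pearson chi-squared test at 0.05.

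The Pain Assessment Protocol sets the population. Eligible teeth were "restorable, symptomatic molar teeth", with a pain threshold but no requirement for a periapical lesion. Both pulp states were treated: "intrapulpal injections were performed for vital teeth and periodontal ligament injections were performed for necrotic teeth". Allocation was by coin toss for the first patient, "followed by an alternating pattern thereafter for the 2 groups", with no stratification by lesion or pulp status. The groups were "GentleWave (GWS) (n=16) or EndoActivator (EA) (n=17"), and 12 and 14 patients respectively were recalled at 12 months.

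**The concern.** A class called healed should mean that disease was present and has gone. Here it also takes in roots that were never diseased. Some such roots are likely: vital teeth were included, and a molar with a lesion on one root may have none on another. These roots say nothing about whether either device helps a lesion resolve, yet they count as successes.

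Two things are at stake. If both arms have a similar share of lesion-free roots, a real device difference is watered down. If the shares differ, the arm that started with more normal roots looks better at recall whatever the device did.

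**Working it through.** The documents give no root count, healing rate, effect size or power for 3Droot, so there is no stated figure to reproduce. The calculation below is an illustration.

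**Inputs from the documents.** 12 v 14 patients recalled (12/16 = 75% and 14/17 = 82% of those allocated); three outcome categories; Pearson chi-squared at 0.05.

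**Assumed inputs.**
- Two or three roots per molar: 24 v 28 or 36 v 42 roots.
- Independent roots. Clustering within teeth is a separate issue.
- Lesion-free roots stay normal and are scored healed.
- Among lesion-bearing roots, 80% v 50% healed (effect) or 50% v 50% (no effect).
- With an effect, the remaining roots split healing/diseased 15%/5% v 30%/20%; with no effect, 30%/20% in both arms.

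**Formula.** With lesion-free share q and true healing p in lesion-bearing roots, P(healed) = q + (1 − q)p. With the same q in both arms, the contrast is (1 − q)(p₁ − p₂).

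**Dilution, true healing 80% v 50%.**

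| q | Scored healed | Contrast |
|---|---|---|
| 0 | 80% v 50% | 30 points |
| 0.25 | 85% v 62.5% | 22.5 points |
| 0.50 | 0.5 + 0.5 × 0.8 = 90% v 0.5 + 0.5 × 0.5 = 75% | 15 points |
| 0.75 | 95% v 87.5% | 7.5 points |

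At q = 0.5 with 36 v 42 roots, the simulated three-category test has about 29% power on all roots and 39% on the lesion-bearing half when the lesion-free counts vary at random. With those counts held fixed it is 27% v 40%; with 24 v 28 roots and fixed counts, 12.5% v 25%. Collapsing to healed v not healed gives 42% v 50% (36 v 42 roots, random counts). In each case, dropping half the roots raises power.

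**Case mix, no device effect (50% healing in both arms), random lesion-free counts.**

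| Lesion-free shares | Scored healed | Three-category rejection, 24 v 28 to 36 v 42 roots |
|---|---|---|
| 50% v 50% | 75% v 75% | near 5% |
| 60% v 40% | 0.6 + 0.4 × 0.5 = 80% v 0.4 + 0.6 × 0.5 = 70% | about 8–9% to 12% |
| 65% v 35% | 0.65 + 0.35 × 0.5 = 82.5% v 0.35 + 0.65 × 0.5 = 67.5% | about 15% to 24% |

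Holding the lesion-free counts fixed lowers the 60% v 40% row to about 5% to 9%. Restricted to lesion-bearing roots, the test rejects about 5% of the time in all these scenarios.

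**The case against.** **The rule may apply only to measured findings.** Volumes are measured first and classes assigned afterwards, so lesion-free roots may never have entered the table. The documents do not report how such roots were scored, and that limit stands. But the text says every individual root was classified, and the only stated condition for healed is met by a root that was always normal. If such roots were left out, the plan should say so.

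**A root that stays normal is a good outcome.** This is fair. An all-root table answers a legitimate question about periapical status at 12 months. It does not answer a question about healing, which is how the outcome is named and tested. Both can be reported.

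**Restriction does not remove all case mix.** Also true: lesion-bearing roots may still differ between arms in initial volume.

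**Stronger readings that the documents do not support.**
- A reader might infer that a root at 0 mm³ before and after also fits the worst category, because its size is unchanged. That category is "diseased (same or larger size finding"), which presupposes a finding. Such a root fits healed only.
- A reader might infer that a cluster-aware model on all roots carries the same bias. Chance imbalance in lesion-free roots is sampling variation, which a valid cluster-aware test allows for. A systematic imbalance would have to be shown to arise from the alternating allocation or from loss to recall, and the documents show none.
- Testing healed v not healed gives higher false rejection with 36 v 42 roots: 17% at 60% v 40% and 33% at 65% v 35%. The plan defines three categories, so those figures do not describe its test.

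**Conclusion.** The concern holds. As written, the rule scores never-diseased roots as healed, and the eligibility criteria make such roots likely. The dilution follows directly from the definition: for any common lesion-free share q, the contrast in healed is multiplied by (1 − q). The illustrated loss, 30 to 15 points and 39% to 29% power, rests on assumed root numbers, healing rates, independence and q = 0.5.

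The false-positive part is conditional. It needs lesion-free shares that differ between arms, which is possible with 12 and 14 patients and no stratification but is not documented. A reader might conclude that the 3Droot result is biased towards one device. The documents do not support that: they give neither the number of lesion-free roots nor their split by arm, so the size and direction of any distortion are unknown.

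**What to change.** Make the 3Droot healing comparison on roots with a preoperative ITK-SNAP volume above zero. This is a baseline criterion, so the filter does not depend on the treatment result. Report lesion-free roots in a separate table as new finding at 12 months, yes or no. Show the number of roots with and without a preoperative finding by arm. The all-root table may stay as a secondary analysis, labelled as periapical status at recall.

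The cost is small: the filter uses a volume already measured and needs no new imaging. The main table will have fewer roots, but in the scenarios above the restricted test has more power, not less.

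### The three ordered healing grades for roots are compared with a chi-squared test that ignores their order and treats roots as independent; an ordinal, patient-level analysis would suit the data better

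*Combined protocol and SAP*

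**What the plan says.** The section *CBCT Healing Assessment and statistical analysis* reports that "Patients (GWS=12, EA=14), were recalled at 12 months postoperative". Periapical volumes before and after treatment were measured, and each root was "assigned a 3Droot classification of either healed (normal PDL around the root at recall), healing (reduced size of finding), or diseased", the last class meaning a finding that was unchanged or larger. The comparison is one sentence: "Pearson's Chi squared test was used to evaluate if there was any difference in 3Droot healing outcomes between the GWS and EA groups". The decision rule is "Results were considered significant if the p≤.05".

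The section does not give the number of roots, expected class proportions, an effect size, a target power, or an effect measure with an interval. It describes no merging of classes and no allowance for roots that share a patient. Three classes in two arms give (3 − 1)(2 − 1) = 2 degrees of freedom.

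**The concern.** The plan's own definitions rank the classes by what happened to the lesion. Pearson's test returns the same p-value however the three labels are shuffled, so that ranking plays no part in the result. Two things follow.

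- **Power.** The test spreads its sensitivity over every way in which two sets of proportions can differ. With 26 patients recalled there is little information to spare.
- **Reading the result.** A significant p-value can come from an arm with more healed and also more diseased roots. No odds ratio or interval is planned that would show a direction.

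The same sentence raises a separate matter. The units are roots of molar teeth, several of which can belong to one patient, and the test assumes that they are independent.

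**Working it through.** The plan has no power figure to reproduce. From the documents: three ordered classes, 12 v 14 patients, a root-level Pearson test, significance at 0.05. Everything else is assumed: 1, 2, 2.5 or 3 analysed roots per patient (12 v 14, 24 v 28, 30 v 35, 36 v 42 roots); EA rates for healed/healing/diseased of 50/30/20, 40/40/20, 60/30/10, 33/34/33 and 70/20/10%; and common odds ratios of 2, 3, 4 and 6.

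**1. Asymptotic loss.** Suppose the whole effect lies along the ordinal score. Both tests then have the same noncentrality λ, about (1.96 + z_power)². The ordinal test needs a statistic above 3.841 (1 df), Pearson's one above 5.991 (2 df). For 60% ordinal power, λ = (1.96 + 0.253)² = 4.90, and the 2-df power is 49.5%.

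| Ordinal power | 2-df power | Loss (points) |
|---|---|---|
| 10% | 8.3% | 1.7 |
| 20% | 15.5% | 4.5 |
| 30% | 23.1% | 6.9 |
| 40% | 31.3% | 8.7 |
| 50% | 40.1% | 9.9 |
| 60% | 49.5% | 10.5 |
| 80% | 70.9% | 9.1 |
| 90% | 83.5% | 6.5 |
| 95% | 90.8% | 4.2 |

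**2. Small-sample loss.** 100,000 simulated tables per scenario, proportional odds, independent roots. Power is Pearson v midrank Wilcoxon, with EA at 50/30/20:

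| Roots | OR 2 | OR 3 | OR 4 |
|---|---|---|---|
| 24 v 28 | 17.4 v 23.7% | 36.4 v 47.2% | 51.4 v 63.9% |
| 36 v 42 | 25.2 v 33.2% | 53.5 v 64.8% | 72.2 v 81.7% |

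At 12 v 14 roots and OR 3 it is about 17 v 26%. Over all the assumed rates, root counts and odds ratios, the loss runs from 2.5 points (36 v 42 roots, EA 33/34/33, OR 6: 95.4 v 97.9%) to about 20 (12 v 14 roots, EA 70/20/10, OR 6). At OR 1 with EA 50/30/20, both tests reject about 5% of the time.

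**3. Two constructed tables, 36 v 42 roots.**

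- *26/6/4 v 20/12/10.* Column totals are 46/18/14. The expected counts are 21.23/8.31/6.46 and 24.77/9.69/7.54, so χ² = 4.92 and p = exp(−4.92/2) = 0.085. The midranks are 23.5, 55.5 and 71.5. W = 26×23.5 + 6×55.5 + 4×71.5 = 1230, against an expected 36×79/2 = 1422. The tie-corrected variance is 126 × (79 − 105,834/6,006) = 7,734, so z = −192/87.9 = −2.18 and p = 0.029.
- *20/4/12 v 20/17/5.* The first arm has more healed roots (20/36 = 56% v 20/42 = 48%) and more diseased roots (12/36 = 33% v 5/42 = 12%). χ² = 10.53, p = exp(−10.53/2) = 0.005. The midranks are 20.5, 51 and 70, W = 410 + 204 + 840 = 1454, the variance is 126 × (79 − 78,096/6,006) = 8,316, z = 32/91.2 = 0.35 and p = 0.73.

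**4. Where the comparison reverses.** At 24 v 28 roots with true rates 40/50/10 v 50/20/30, Pearson has 62.6% power and Wilcoxon 5.6%.

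**5. Clustering.** Null rejection at nominal 5%, with 12 v 14 patients and correlated roots (latent normal model, 40,000 trials):

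| Roots per patient | Latent correlation | Pearson | Wilcoxon |
|---|---|---|---|
| 2 | 0.2 / 0.4 / 0.6 | 6.4 / 8.3 / 10.3% | 6.8 / 8.6 / 11.1% |
| 3 | 0.2 / 0.4 / 0.6 | 7.8 / 11.0 / 15.5% | 8.6 / 12.3 / 16.5% |

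Repeat runs for Pearson with three roots reached about 17% at the highest correlation.

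**6. The proposed test.** Wilcoxon with arm permuted by patient, three roots each, EA 50/30/20. Null rejection is about 5%. At OR 3, power over repeat runs is about 48-53%, 41-44% and 37-39% for correlations 0.2, 0.4 and 0.6. The root-level chi-squared rejects about 52-58% of the time, but part of that is its inflated null rejection.

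**The case against.** The strongest defence is the stated aim, "any difference in 3Droot healing outcomes", which a 2-df test answers. Where the authors wanted a direction they wrote one: *Pain Assessment Statistical Analysis* asks whether pain fell more often in one group than in the other. A reader might infer that the 3Droot question is which system heals better, so that the test is wrong. The documents do not say that. This part of the defence stands: the choice costs efficiency and interpretability and is not a validity error. It does not remove the point, because a comparison of graded healing with no effect measure can end in a significant result that names no better arm.

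A reader might also infer a fixed cost of about 10 points of power. That cannot be derived from the documents, which give no rates, root counts, effect size or target power. The loss depends on all of these and becomes a gain when the arms differ mainly in the middle class. Nothing in the plan supports assuming proportional odds.

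Nor do the root-level gains show what the team would see on changing the analysis. They assume independent roots, and the proposed test is built for roots that are not. Against the present root-level chi-squared, it will often look less powerful. Finally, an ordinal test on roots alone would leave the inflated type I error in place.

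**Conclusion.** The point holds in conditional form. An ordered outcome is tested without its order, and under a monotone shift that loses power: about 9 to 10.5 points asymptotically when ordinal power is roughly 40-80%, less outside that band, and about 2.5 to 20 points in the small-sample scenarios. All of this rests on assumed inputs and independent roots. A significant result may favour neither arm.

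The type I problem in the same sentence comes from the unit of analysis and not from ignoring order. Its size, about 8-17% for Pearson and similar for a root-level Wilcoxon test, assumes three analysed roots per patient and a latent correlation of 0.2 to 0.6. With two roots it is smaller. The two matters should be dealt with together.

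**What to change.** For 3Droot, replace the root-level chi-squared with one of the following:

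- a Wilcoxon or linear-by-linear score test on the three ordered classes, with the p-value from permuting arm among patients and all roots of a patient kept together; or
- a proportional-odds model with a patient random effect.

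Report the common odds ratio with its interval, and state the number of roots and of patients in each arm. As the plan describes recall as already done, label this a revised analysis and show the original chi-squared beside it.

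The cost is analysis code only; no new data are needed. There are two downsides to state. The ordinal test has little power for differences mainly in the middle class, as step 4 shows. Its p-value may also be less favourable than the present one, because clustering is now counted. One assumption should be written down: *Pain Assessment Protocol* allocates by one coin toss and then alternation, so permuting patients relies on their being exchangeable and not on the allocation procedure itself.
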